#### 2.1.1 Levonorgestrel (LNG)

Levonorgestrel is a progestational agent that inhibits ovulation by interrupting follicular development, and inhibits fertilization by altering the tubal transport of sperm and/or ova. In addition, it may inhibit implantation by altering the endometrium, but it is not effective once the process of implantation has begun [21]. LNG is commonly used in combination oral contraceptive pills, as EC, in progestin-releasing subdermal implants, and intrauterine devices. As EC, LNG should be taken within 72 hours after unprotected intercourse to prevent pregnancy. The absolute effectiveness of EC is difficult to determine because the rate varies with the timing of dosage with respect to unprotected intercourse, ovulation, and with the type of EC used. Estimates of LNG efficacy range from 59-94% [22]. In a multicenter randomized comparison of LNG versus ulipristal in nearly 1700 women presenting to family planning clinics for EC, there were 37 pregnancies with no statistical difference observed between the groups. To increase the power of the study, a meta-analysis was performed, and data from a total of 2221 women randomized to either ulipristal or LNG were compiled. This analysis confirmed that the pregnancy rate in both groups was lower than predicted, and that the pregnancy rate for LNG was 2.6% [23].

LNG for EC is typically given as a single 1.5 mg dose within 72 hours after intercourse. LNG reaches maximum concentration approximately 1.7 (range 1-4)

hours after administration and is 100% bioavailable after oral administration [21, 24, 25]. In 30 healthy, female volunteers, the mean (SD) LNG  $C_{max}$  was 19.1 (9.7) ng/mL, area under the curve  $(AUC)_{inf}$  was 307.5 (218.5) ng\*hr/mL, and half-life was 27.5 hours [21]. A clinical evaluation of another formulation of LNG (0.75 mg tablets, two tablets once) in five healthy volunteers found a geometric mean 44-hour (39-48-hours) half-life [26].

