The effect of food on LNG absorption has not been evaluated. LNG is 97.5-99% protein-bound to sex hormone-binding globulin and albumin, only 2% of LNG is present as unbound drug. This, in addition to an inverse association between LNG concentrations and body weight [27-29], contributes to the high interpatient variability in drug levels. LNG is extensively metabolized to inactive metabolites via the cytochrome P450 (CYP) enzyme system, specifically the CYP3A4 isoenzyme, and co-administration of medications that induce or inhibit CYP3A4 are known to impact LNG concentrations. Approximately 45% of LNG and its metabolites are excreted in the urine and 32% in the feces, and the elimination half-life following a single oral dose LNG is approximately 17 to 24 hours. LNG is not known to influence exposure to ART or TB therapy [21].

LNG PKs are influenced by body weight as measured by BMI. Two studies have evaluated the effect of an overweight or obese BMI on LNG PKs. Edelman et al. found 49% lower  $AUC_{0-2.5h}$  in women with BMI >35 compared to BMI <25 [30]. Pradipan et al. found 52% lower  $AUC_{0-24h}$  in women with BMI >30 kg/m^2 compared to BMI <25 kg/m^2 [31].

Studies have not been conducted to determine the PK parameter that is associated with LNG EC effectiveness. Variable doses of LNG EC have been evaluated, ranging from 0.4 to 1.5 mg, and the studies conducted were not designed to be dose-finding. Therefore, the concentration-response relationship is unknown [32]. Although there is a proposed threshold for LNG implant effectiveness, the mechanism of contraception is not the same between a long-acting contraceptive and EC so this concentration cannot be extrapolated to EC.

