### 10.4 Sample Size and Accrual [53, 78-80]

Given that a therapeutic target for minimum exposure required or average exposure expected for single dose use of LNG as emergency contraception (EC) is unknown, this study is estimating whether adjusted dosing of LNG under a known DDI achieves similar exposure to LNG single dose as measured by the geometric mean ratio (GMR) of the AUC of LNG concentrations over the 8 hours post dose. The study design was developed under the constraints of requiring a parallel groups design (rather than a crossover design using healthy controls), practicalities of number of available participants to enroll and complete the study in a reasonable timeframe, and how the features of this highly variable drug (LNG) result in both power to test for bioequivalence as defined by a specified interval about equivalence, and precision of GMR estimates by the width of the 90% confidence interval.

The effective sample sizes of 30 women in Groups B-D and 15 women in Group A were chosen to provide adequate statistical precision about the estimated GMR, which compares arms in order to address the primary study objectives [54]. See below for the total sample size enrollment, which includes how these effective samples sizes are inflated slightly to accommodate missing primary outcome data.

Table 10.4-1: Sample size per arm (prior to inflation for replacements)

Assumptions: Sample size required to give 80% probability (power) to conclude bioequivalence defined as the 90% CI for the GMR being entirely within the No-effect Bounds (NEB). Various NEBs are provided for BE given that bounds of (80%, 125%) may be considered too conservative for highly variable drugs with a wide therapeutic ranges in PK exposure. [Note: Calculations use 5% significance level with two, one-sided tests (TOSTs) testing procedure.]

Sample Sizes per Arm in Table	Coefficient of Variation Estimates*								
	0.45			0.70			0.90		
Alternative Hypothesis (True GMR):	100%	95%	90%	100%	95%	90%	100%	95%	90%
NEB : (67%,150%)	20	22	27	43	45	57	63	67	84
NEB : (70%,143%)	26	28	37	55	59	79	81	87	117
NEB : (75%,133%)	40	45	72	85	97	154	126	144	228

\*Note: CV for AUC(0-24hr) ranged from 0.45 to 0.90 in the individual arms of PK study of LNG-EC and St. John's Wort (Time period 1 when LNG-EC given alone, ref ct.gov NCT00131885). Package insert for LNG CV(AUC24hr)=0.7. Data not available for CV of AUC or LNG-EC under shorter time frames.

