### 10.6.3 Secondary Outcomes Analysis

The secondary objective of comparing increased dose of LNG EC to standard-dose among women on EFV (randomized comparison), will use analyses parallel to the primary outcome analysis as described above. However, since the hypothesis for this objective is superiority (rather than equivalence), the statistical inference for examination of the confidence interval about the GMR will focus whether this interval includes or excludes 1 (in which a significance difference can be concluded). Conclusions will focus on the estimations and plausible values of the GMR between LNG doses within this EFV comparison. Note this comparison is not subject to confounding because it is randomized comparison. A similar, non-randomized comparison will be performed between randomized Group A and control, directly assigned Group C.

Analyses for other PK parameters of LNG will follow an analysis plan parallel to the primary outcome as described above. Note that derivation of these PK parameter outcomes are according to specifications in [section 11.0](#) below.

Other adverse events (that do not meet the primary safety outcome) and side effects between single dose and double dose may be compared either separately by group, or collapsed over group by LNG dosing (single vs. double).

Further details are outlined in the study's Statistical Analysis Plan (SAP).

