### 11.3 Primary and Secondary Data, Modeling, and Data Analysis

#### LNG analysis

The PK parameters for LNG include: maximum concentration ( $C_{max}$ ), time to maximum concentration ( $T_{max}$ ), minimum concentration ( $C_{min}$ ), **time to minimum concentration ( $T_{min}$ )**, oral clearance (CL/F), volume of distribution (Vd), elimination half-life ( $T_{1/2}$ ), and area under the concentration-time curve over 8 hours ( $AUC_{0-8h}$ ), 24 hours ( $AUC_{0-24h}$ ), 48 hours ( $AUC_{0-48h}$ ), and to infinity ( $AUC_{inf}$ ). Standard noncompartmental techniques will be used to determine these PK parameters using the software package Phoenix WinNonLin (Certara®). The AUC (including the primary outcome) will use the linear up/log down version of the trapezoidal rule. This version of the trapezoidal rule uses linear interpolation between untransformed data up to  $C_{max}$ , and between log-transformed data from  $C_{max}$  through  $C_{last}$  [81, 82].  $C_{max}$  will be taken as the maximum observed concentration.  $T_{max}$  is the time at which  $C_{max}$  occurs.  $C_{min}$  will be taken as the minimum observed concentration after the observed dose. Apparent oral clearance will be calculated as  $CL/F = \text{dose}/AUC_{0-24}$  or  $CL/F = \text{dose}/AUC_{0-48}$ . The  $T_{1/2}$  will be determined using regression analysis when possible.

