3.2.2 Secondary LNG PK Parameters

Title: LNG PK Parameters calculated based on intensive LNG PK samples obtained from individual participants

Descriptions:

Note: Unless otherwise indicated, standard noncompartmental techniques were used to determine the PK parameter using the software package Phoenix WinNonLin (Certara®).

C_{max}: C_{max} for each participant was the maximum observed concentration.

C_{min}: C_{min} for each participant was the minimum observed concentration after the observed dose among post-dose concentrations. Assay lower limit of quantification for LNG was 0.025 ng/mL; values < LLOQ were imputed as 0.0125.

CL/F: Apparent oral clearance (CL/F) was calculated from the observed LNG concentration from LNG PK samples at pre-dose through 48 hours post-dose. Assay lower limit of quantification for LNG was 0.025 ng/mL; values < LLOQ were imputed as 0 (if pre-dose) or as 0.0125 (if post-dose).

V_d: Volume of distribution (V_d) was calculated for each participant from observed LNG concentration from LNG PK samples at pre-dose through 48 hours post-dose.

T_{1/2}: T_{1/2} for each participant was calculated from the observed LNG concentration from LNG PK samples at pre-dose through 48 hours post-dose. Assay lower limit of quantification for LNG was 0.025 ng/mL; values < LLOQ were imputed as 0 (if pre-dose) or as 0.0125 (if post-dose).

T_{min}: T_{min} for each participant was time to the minimum observed LNG concentration after the observed dose.

Other AUC: AUC for each participant was from LNG concentrations calculated over 24 or 48 hours and modeled to AUC_{infinity} using the linear up/log down version of trapezoidal rule (i.e., noncompartmental technique). This version of the trapezoidal rule uses linear interpolation between untransformed data up to C_{max}, and between log-transformed data from C_{max} through C_{last}. Assay lower limit of quantification for LNG was 0.025 ng/mL; values < LLOQ were imputed as 0 (if pre-dose) or as 0.0125 (if post-dose).

Time Frame: Intensive LNG PK samples within 30 minutes pre-dose, and 0.5, 1, 1.5, 2, 3, 4, 6, and 8, 24 and 48 hours post-dose [adjusting to appropriate time frame above]

Analysis Population: Participants with PK concentrations over 24 or 48 hours and who took both assigned doses of LNG study treatment and expected doses of ART or TB therapy.

Reporting Groups: A-D

Associated study objectives: Primary Objectives 1 and 2, Secondary Objectives 1 and 2

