Descriptive Summary Statistics per group:

- **Original scale: n, mean, sd, CV, median, Q1, Q3, min, max**
- **Natural log scaled: geometric mean, 95% CI on GM**

Statistical Analysis Summary: Tables parallel to the Summary table for the primary outcome will be produced for subset of secondary PK parameters, which are based on LNG concentrations. The same reference interval will be used as a comparison for these additional PK parameters. PK parameters not formulated from LNG concentrations (e.g. Tmax, Terminal half-life) will only have descriptive summary statistics.

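### Single-dose CL/F is defined with a truncated AUC (0–24 or 0–48 h), which overstates clearance, and the documents do not keep CL/F out of the 0.70–1.43 comparison

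*Protocol*

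**What the plan says.** CL/F and Vd are named secondary outcomes in Protocol 10.2.2.2, and SAP 1.1 says secondary results will be posted on ClinicalTrials.gov.

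- **Formula.** Protocol 11.3 (LNG analysis): "Apparent oral clearance will be calculated as" dose/AUC0-24 or dose/AUC0-48. No rule chooses between the two. The same section lists AUCinf among the parameters to be derived.
- **SAP entry.** SAP 3.2.2 says CL/F "was calculated from the observed LNG concentration from LNG PK samples at pre-dose through 48 hours post-dose". It does not name the AUC in the denominator.
- **Comparison.** Protocol 10.6.3: "Analyses for other PK parameters of LNG will follow an analysis plan parallel to the primary outcome as described above". SAP 3.2.2 narrows this: tables like the primary one "will be produced for subset of secondary PK parameters, which are based on LNG concentrations", and "The same reference interval will be used as a comparison for these additional PK parameters". The subset is not listed. Tmax and terminal half-life are given as examples of parameters that are only described.

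**The concern.** There are two problems, one certain and one conditional.

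**The formula.** Each woman takes one dose, so there is no steady-state interval over which dose/AUC would equal CL/F. The numerator is the whole dose and the denominator leaves out everything after 24 or 48 h, so CL/F is too high in every group. If EFV or RIF raises systemic clearance, the half-life shortens and the window captures more of AUCinf in the induced group than in the control group. The clearance ratio is then pulled toward 1. If induction lowers only bioavailability, the captured share is equal and the ratio is unbiased.

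**The bounds.** SAP 2.3 justifies 0.70–1.43 for similarity of LNG exposure. Groups B and D receive twice Group C's dose. If CL/F enters the same table, equal exposure corresponds to a CL/F ratio of 2, not 1. For A versus C, the SAP 3.1 criterion that the interval lies below 1 points the wrong way for clearance.

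At stake are the posted clearance values and how readers judge the size of induction.

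**Working it through.** **The plan's own figure.** The documents state no CL/F figure. The one figure tied to the bounds is the 88% power in SAP 2.3 (n = 30 per group, CV 0.45, true GMR 1.00, bounds 0.70–1.43). With SD = √ln(1 + 0.45²) = 0.429 and 58 df, exact two one-sided tests give 87.6% and the normal approximation 88.5%. It reproduces.

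**Inputs from Protocol 2.1.1.** After 1.5 mg, mean Cmax is 19.1 ng/mL and mean AUCinf 307.5 ng·h/mL, so CL/F = 1500/307.5 = 4.88 L/h. Half-life is 27.5 h in that study. Elsewhere in the same section: "the elimination half-life following a single oral dose LNG is approximately 17 to 24 hours", and another formulation "found a geometric mean 44-hour (39-48-hours) half-life".

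**Size of the truncation.** Overstatement = AUCinf/AUC0-t.

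The model is a two-compartment oral model with CL/F 4.88 L/h. Volumes are solved to match Cmax 19.1 and a terminal half-life of 17, 20, 24, 27.5, 35 or 44 h. Assumed: ka 1.0, 1.5 or 2.5 per h and inter-compartmental clearance 5, 8 or 12 L/h (54 fits).

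| Quantity | 0–24 h | 0–48 h |
|---|---|---|
| Share of AUCinf captured, control | 0.455–0.696 | 0.627–0.886 |
| CL/F overstatement, control | 1.44–2.20 | 1.13–1.60 |
| Share captured, clearance doubled | 0.656–0.874 | 0.815–0.976 |
| Apparent ratio when the truth is 2.0 | 1.39–1.59 | 1.54–1.82 |

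The apparent ratio is 2 × control share / induced share, taken fit by fit. By half-life, the 48 h overstatement is 1.13–1.15 (17 h), 1.22–1.28 (24 h), 1.25–1.34 (27.5 h) and 1.40–1.60 (44 h).

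A one-compartment model with Tmax 1.7 h gives more bias: 1.6–3.2-fold at 24 h and 1.17–1.89-fold at 48 h.

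**The bounds, if CL/F is included.** Over one AUC window,

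GMR(CL/F) = (3.0/AUC_B)/(1.5/AUC_C) = 2/GMR(AUC), and likewise for D versus C.

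The AUC bounds map to 2/1.43 = 1.40 and 2/0.70 = 2.86. Only 1.40–1.43 of that range lies inside 0.70–1.43.

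Illustration: the 57% AUC reduction with EFV in Protocol 2.2 (healthy volunteers on a different LNG regimen), dose-proportionality assumed. B/C: AUC ratio 2 × 0.43 = 0.86, CL/F ratio 2/0.86 = 2.33. A/C: AUC ratio 0.43, CL/F ratio 1/0.43 = 2.33. The 90% intervals are GMR × exp(± t × SD × √(1/n₁ + 1/n₂)), with 58 df for 30/30 and 43 df for 15/30. The CVs come from Protocol 10.4, where "CV for AUC(0-24hr) ranged from 0.45 to 0.90".

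| CV (SD) | B/C AUC | B/C CL/F | A/C AUC | A/C CL/F |
|---|---|---|---|---|
| 0.45 (0.429) | 0.71–1.04 | 1.93–2.80 | 0.34–0.54 | 1.85–2.92 |
| 0.70 (0.631) | 0.65–1.13 | 1.77–3.05 | 0.31–0.60 | 1.66–3.25 |
| 0.90 (0.770) | 0.62–1.20 | 1.67–3.24 | 0.29–0.65 | 1.54–3.50 |

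At CV 0.45, B/C meets the bounds on AUC while its CL/F interval lies wholly above 1.43. For A/C the AUC intervals lie below 1 and the CL/F intervals above 1 at every CV.

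**The case against.** **The subset may already exclude CL/F.** SAP 3.2.2 treats terminal half-life as not formulated from LNG concentrations, yet describes its calculation in nearly the same words as CL/F. The subset could therefore mean measures on a concentration scale (Cmax, Cmin, AUCs), and the Analysis Implementation Plan, which is not available here, may settle it. This stands as a limit: the bounds problem is conditional. Its intervals illustrate the algebra and are not evidence that CL/F will be tested. But neither document excludes CL/F, so the subset still needs listing.

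**The SAP may intend dose/AUCinf.** It invokes standard noncompartmental methods, and the 0–48 h wording may say only which samples are used. That reading is possible, but the SAP does not withdraw the protocol's formula.

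**The size depends on the model.** True: ka and inter-compartmental clearance are assumed, and one study's means are combined with half-lives from other sources. The direction is certain and the one-compartment model gives more bias, but the ranges are not bounds.

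**An observed window is practical.** Women who miss the 24 h and 48 h visits stay on study, and the terminal slope will not always be estimable. That is a fair reason to allow one fixed, labelled window, but not an unresolved choice between two.

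**Conclusion.** The formula in Protocol 11.3 is wrong as written for a single dose. It overstates CL/F in every group, by about 1.13–1.60-fold with AUC0-48 and 1.44–2.20-fold with AUC0-24 under the two-compartment assumptions. It understates the between-group ratio to the extent that induction acts on systemic clearance. The conclusion rests on this part.

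The bounds problem holds only if CL/F is in the SAP's unlisted subset. Changing to AUCinf would not cure it, because it comes from the twofold dose ratio.

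Severity is minor. The primary AUC0-8h comparison, its bounds and the sample size are untouched.

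**What to change.** - **Protocol 11.3 and SAP 3.2.2:** define CL/F = dose/AUCinf and derive Vd from the same AUCinf. Report the extrapolated fraction, and do not report CL/F or Vd where the terminal slope cannot be fitted. If an observed-window value is kept, use one window for all women and label it dose/AUC0-48.
- **SAP 3.2.2, Statistical Analysis Summary:** list the subset. Limit the 0.70–1.43 comparison to exposure measures (Cmax, AUC0-24, AUC0-48, AUCinf). Give CL/F and Vd GMRs with intervals but without similarity or directional criteria.

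**Cost.** Wording only, no new data. Some women will lack CL/F, and the slope will rest on the 8, 24 and 48 h samples. In noise-free curves from the same model at the planned times, 9.5–26.5% of AUCinf is extrapolated in controls and 2–14% with clearance doubled. The remaining control overstatement is at most 1.18-fold. A true ratio of 2.0 is recovered as 1.76–2.00, against 1.54–1.82 with dose/AUC0-48, and is closer at every half-life tested. Assay noise would widen these ranges and was not quantified.

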#### ART or RIF exposure in plasma

EFV, DTG, or RIF will be quantitated from aliquots of the same samples collected to assess LNG according to [section 6.3.9](#). The concentrations will be at a single time point; therefore, no PK parameters will be calculated.

For participants receiving EFV: EFV will be measured in a plasma sample collected 12-20 hours after the last dose of EFV. Efavirenz should be administered in the evening prior to PK visits.

For participants receiving DTG or RIF: DTG or RIF will be measured in a plasma sample collected 20-28 hours after the last dose of DTG or RIF. If DTG or RIF is being administered in the morning, the pre-LNG dose sample at entry should be collected prior to administration of DTG or RIF.

See MOPS for further discussion of dose timing in relation to PK sampling at entry.

#### Hair analysis

Hair levels will be evaluated as continuous variables, possibly using logarithmic transformation if their distribution is skewed. Values below the detection limit will be counted as equal to the detection limit. We will examine scatterplots and calculate Spearman correlation coefficients for hair levels with plasma concentrations, we will also examine the correlation between SNPs in the genes implicated in EFV metabolism (e.g., CYP2B6) and hair concentrations of EFV.

#### Pharmacogenetic analyses

For all study participants who provide DNA for genetic testing, assays will be performed for polymorphisms in genes relevant to study drugs and concomitant medications (e.g., CYP2B6/CYP2A6 SNPs for efavirenz, UGT1A1 for dolutegravir). Associations will be explored between selected genetic polymorphisms and outcome measures as described in [section 10.0](#).

### 11.4 Anticipated Outcomes

These PK studies will provide information on plasma concentrations of LNG when used as EC in participants taking EFV or RIF. The PK data for LNG will fill gaps in our knowledge, about possible EC options in women receiving EFV-based ART and RIF-based TB treatments.

## 12.0 DATA COLLECTION AND MONITORING

### 12.1 Records to Be Kept

Electronic case report form (eCRF) screens will be made available to sites for data entry. Participants must not be identified by name on any data submitted to the DMC. Participants will be identified by the patient identification number (PID) and study identification number (SID) provided by the ACTG DMC upon randomization/registration.

### 12.2 Role of Data Management

12.2.1 Instructions concerning entering study data on eCRFs will be provided by the ACTG DMC. Each CRS is responsible for keying the data in a timely fashion.

12.2.2 It is the responsibility of the ACTG DMC to assure the quality of computerized data for each ACTG study. This role extends from protocol development to generation of the final study databases.

### 12.3 Clinical Site Monitoring and Record Availability

12.3.1 Site monitors under contract to the NIAID will visit participating clinical research sites to review the individual participant records, including consent forms, eCRFs, supporting data, laboratory specimen records, and medical records (physicians' progress notes, nurses' notes, individuals' hospital charts), to ensure protection of study participants, compliance with the protocol, and accuracy and completeness of records. The monitors also will inspect sites' regulatory files to ensure that regulatory requirements are being followed and sites' pharmacies to review product storage and management.

12.3.2 The site investigator will make study documents (e.g., consent forms, drug distribution forms, eCRFs) and pertinent hospital or clinic records readily available for inspection by the local IRB, the site monitors, the FDA, the NIAID, the OHRP, other local, US, and international regulatory entities for confirmation of the study data.

